5.5.2 Potential Adverse Events

The potential adverse events include:

1. Systemic hypotension
2. Abnormal cranial imaging consistent with intracranial bleed
3. Arrhythmias
4. Extracranial bleeding (especially pulmonary and gastrointestinal hemorrhage)
5. Renal dysfunction
6. Respiratory deterioration
7. Other events that are deemed severe (or worse in intensity), and either unexpected or at least possibly related to study or results in death

The data regarding serious adverse events will be reviewed after recruitment of the first 10 subjects. Subsequently, data regarding adverse events will be reviewed every 17 subjects (25% of the sample size). If DSMC is concerned about adverse events, the subjects can be unmasked for the DSMC to assess whether the event rates appear to differ between treatment arms. Should there be excess serious adverse events in one group, the committee may recommend breaking of the blinding and discontinuation of enrollment.

5.5.3 Interim Monitoring Plan and Stopping Rules

As mentioned previously, the DSMC will meet as per the following plan. A suggested schedule may include meeting after the first 10 subjects are enrolled and at 25% (~ 17 subjects), 50% (33 subjects), 75% (~ 50 subjects) of target sample size and after completion of enrollment.

In addition to monitoring trial progress, the DSMC will also review accumulating safety data for the trial. All safety data presented to the DSMC will be blinded to treatment group, though the report may be unmasked at the DSMC's request.

The three main adverse events that require close monitoring include severe hypotension , hemorrhage (intracranial and extracranial) and arrhythmia or death due to severe hypotension or intracranial hemorrhage or arrhythmia while on study drug infusion or 24 hours after cessation of study drug infusion.

The presence of the following adverse events *possibly, probably or definitely due to the study drug* in > 20% of subjects after enrollment of 33 patients with a statistically significant difference between the treatment arm and the placebo arm can lead to a discussion at DSMC regarding cessation of the trial.

- (a) Severe hypotension is defined by a decrease in mean blood pressure > 20 to 30 mmHg compared to baseline OR receiving extensive volume therapy (>40 to 80 ml/kg during a 24 hour period of the study monitoring period OR escalation of vasoactive inotropic score by >20 to 30 compared to baseline) The study monitoring period is the time on study drug therapy and within 24 hours of completion of study drug therapy.
- (b) Life-threatening hypotension - receiving volume therapy > 80 ml/kg during a 24 hour period of the study monitoring period OR escalation of vasoactive inotropic score by > 30 compared to baseline
- (c) Severe intracranial hemorrhage (unilateral or bilateral blood/ echodensity filling the ventricle(s) resulting in distension without parenchymal bleeding and without a midline shift) while on study drug therapy and within 24 hours of completion of study drug therapy.
- (d) Life-threatening intracranial hemorrhage - Parenchymal hemorrhage/ echodensity (including cerebellar hemorrhage) and / or any bleed/ echodensity associated with a midline shift.
- (e) Severe arrhythmia – heart rate rhythm abnormality including bradycardia (heart rate ≤ 70/min) or tachycardia (heart rate 220 to 300/min) OR treated with anti-arrhythmic medications and no use of pacing, cardioversion or defibrillation OR associated with a 5 to 10 mm Hg decrease in MBP from the time prior to the onset of arrhythmia
- (f) Life-threatening arrhythmia - tachyarrhythmia with heart rate > 300/min OR treated with pacing, cardioversion or defibrillation OR associated with a > 10 mm Hg decrease in MBP from the time prior to the onset of arrhythmia
- (g) Death – resulting from severe hypotension, hemorrhage or arrhythmia.

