3.5. POTENTIAL RISKS AND BENEFITS TO SUBJECTS

Infants with CDH represent a high-risk population with mortality ranging from 30 to 40%. Additional risks from the use of IV milrinone include systemic hypotension, intracranial hemorrhage (reported in critically ill neonates with PPHN) and arrhythmias (reported in adults). The anticipated benefit is improvement in oxygenation and reduced need for ECMO.

Systemic hypotension is commonly seen in patients with CDH. In recent studies 80-90% of patients with CDH required treatment with vasoactive medications. (Snoek, Capolupo et al. 2016) Patients will be closely monitored for systemic hypotension due to its association with increased right –to-left shunting and hypoxemia. Study drug will be discontinued in the presence of 'severe' or 'life-threatening' systemic hypotension as outlined in the MOP that cannot be explained by other causes (such as sepsis or pneumothorax) and described below.

- a. Severe hypotension:
 - decrement in mean BP > 20 to 30 mmHg compared to the most recent value during the period prior to study drug or at baseline OR
 - receiving extensive volume therapy (40 to 80 ml/kg during a 24-hour period of the study monitoring period: onset of study drug to 24 hours after discontinuation of study drug) OR
 - escalation of vasoactive inotrope score by 20 to 30 compared to the score at baseline
- b. Life-threatening hypotension:
 - Decrease in mean BP > 30 mmHg compared to the most recent value during the period prior to study drug or at baseline OR
 - receiving volume therapy (> 80 ml/kg during a 24-hour period of the study monitoring period: onset of study drug to 24 hours after discontinuation of study drug) OR
 - escalation of vasoactive inotrope score by > 30 compared to the score at baseline)

(i) Vasoactive inotrope score calculation (vasoactive inotrope score = dopamine dose ($\mu\text{g}/\text{kg}/\text{min}$) + dobutamine dose ($\mu\text{g}/\text{kg}/\text{min}$) + epinephrine dose ($\mu\text{g}/\text{kg}/\text{min} \times 100$) + norepinephrine dose ($\mu\text{g}/\text{kg}/\text{min} \times 100$) + phenylephrine dose ($\mu\text{g}/\text{kg}/\text{min} \times 100$) + vasopressin dose ($\text{U}/\text{kg}/\text{min} \times 10000$) (Gaies, Gurney et al. 2010)

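### The synopsis and the Section 4.2.5 Dose text give opposite escalation instructions for some infants, and the Section 5.5.3 event list omits two kinds of event that Section 3.5 grades as severe or worse

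*Combined protocol and SAP*

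**What the plan says.** **Escalation.** The infusion starts at 0.33 µg/kg/min and may step up to 0.66 µg/kg/min at 2 to 4 h. The synopsis (Study Intervention/Methods) withholds the step for hypotension, which it defines by two findings joined with *and*: mean BP below 35 mmHg and a vasoactive inotrope score above 30. Section 4.2.5 (Dose) allows the step only if mean BP has not been below 35 mmHg for 30 minutes or more and the score is 30 or less. The Figure 6 legend, also in Section 4.2.5, allows it if there are no adverse effects and gives the two findings in brackets.

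**Hypotension events.** Section 3.5 lists alternative ways to reach the life-threatening grade, the first being "Decrease in mean BP > 30 mmHg compared to the most recent value during the period prior to study drug or at baseline OR" one of the volume or score limbs. In Section 5.5.3, item (a) covers a mean BP fall of more than 20 and up to 30 mmHg, with volume and score alternatives. Item (b) reads "Life-threatening hypotension - receiving volume therapy > 80 ml/kg during a 24 hour period of the study monitoring period OR escalation" of the score by more than 30. It has no blood-pressure limb.

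**Extracranial bleeding.** Section 5.5.3 names among the main events "hemorrhage (intracranial and extracranial) and arrhythmia". Section 3.5 defines severe and life-threatening extracranial bleeds and stops study drug for them. In the Section 5.5.3 list, the hemorrhage items (c) and (d) are both intracranial. Extracranial bleeding can enter only through item (g), death "resulting from severe hypotension, hemorrhage or arrhythmia".

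**The concern.** Safety is Specific Aim 2, and the exclusion criteria themselves describe the hypotension risk as high during the first 24 hours of study drug. The escalation step falls inside that period, so two parts of one protocol should not give opposite instructions for the same infant. The hypotension exclusion does not remove these infants, because it too requires low pressure and a high score together.

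The Section 5.5.3 list defines which drug-related events count towards the DSMC discussion trigger. If a larger pressure fall drops out while a smaller one counts, or if a named main event has no non-fatal entry, the count does not measure what the section says it monitors.

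**Working it through.** The point concerns definitions, so the plan has no figure to reproduce. The rules are compared case by case.

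**1. Escalation rules**

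| Mean BP <35 for ≥30 min | Score >30 | Synopsis | 4.2.5 Dose text |
|---|---|---|---|
| no | no | escalate | escalate |
| no | yes | escalate | hold |
| yes | no | escalate | hold |
| yes | yes | hold | hold |

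The rules differ in 2 of 4 cells, and in both the synopsis doubles a dose that the Dose text holds.

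*Who is affected.* Section 3.5 stops study drug for severe hypotension not explained by another cause: a mean BP fall above 20 mmHg, a score rise of 20 or more, or 40 ml/kg or more of volume in 24 h. Escalation arises only for infants who have not met this.
- Mean BP 32, score 10: no fall above 20 mmHg if the pre-drug value was 32 + 20 = 52 mmHg or less.
- Mean BP 40, score 35: no rise of 20 if the baseline score was above 35 − 20 = 15.
- Either finding with another cause for the hypotension.

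*Exposure over a full 72 h course in the milrinone arm* (rate × 60 × hours, weaned at 70 h if escalated):
- Held: 0.33 × 60 × 72 = 1425.6 µg/kg.
- Escalated at 2 h: 39.6 + 0.66 × 60 × 68 + 39.6 = 2772.0 µg/kg; ratio 2772.0/1425.6 = 1.94.
- Escalated at 4 h: 79.2 + 0.66 × 60 × 66 + 39.6 = 2732.4 µg/kg; ratio 1.92.

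*Steady state* (rate ÷ clearance, neonatal clearances in Table 4):
- At 1.83 mL/kg/min: 180 ng/mL at 0.33 and 361 ng/mL at 0.66 µg/kg/min.
- At 1.64 mL/kg/min: 201 and 402 ng/mL.

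**2. Isolated mean BP fall**, for events judged at least possibly drug-related. Both infants receive 30 ml/kg of volume, and the score goes from 10 to 25 (a rise of 15), so no volume or score limb is met.

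| Mean BP | Fall (mmHg) | Section 3.5 | 5.5.3(a) | 5.5.3(b) |
|---|---|---|---|---|
| 62 to 37 | 25 | severe | met | not met |
| 62 to 30 | 32 | life-threatening | not met | not met |

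This looks like an omission, not a choice: life-threatening arrhythmia in item (f) keeps its own blood-pressure limb, as in Section 3.5.

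**3. Non-fatal extracranial bleed.** A bleed graded severe or life-threatening in Section 3.5 matches none of items (a) to (f), and (g) requires death.

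**The case against.** **Escalation.** Many infants in the two conflicting cells would already be off drug under Section 3.5, and the clinical team may stop study drug at any time. A reader might infer that every infant with one abnormal finding is at risk of a doubled dose; the stop criteria do not support that. The 1.9 ratio is a ceiling. Treatment ends earlier after two OI values below 7, and a held infant might still qualify within the 2 to 4 h window. The Figure 6 legend can be read either way, since *no adverse effects* may mean that neither finding is present. It could also be said that the detailed section governs an abbreviated synopsis, but the protocol does not say so and the legend does not settle it. These points narrow the conflict without removing it.

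**Event list.** A reader might infer that the DSMC would not see these events. The documents do not support that. Section 5.5.1(vi) sends every serious, at least possibly related event to the DSMC Chair. Section 5.5.2 lists hypotension and extracranial bleeding and lets the committee act on an excess. The Section 5.5.3 trigger only opens a discussion. A fall above 30 mmHg may also meet another limb, and a committee would be unlikely to ignore it. This objection largely stands and limits the weight of points 2 and 3.

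**Further inferences not supported.**
- *That one uncounted infant would decide the trigger.* This needs an assumed arm split, test, denominator and placebo event count. With 17 versus 16 infants and Fisher's exact test, significance needs 5 milrinone events with no placebo event (p = 0.044), but 7 with one (p = 0.039).
- *That bleeds first seen on a scan 24 to 96 h after drug go unreported.* The text is unclear here, because Section 5.5.1 times entry from discovery.
- *That differences at exactly 40 ml/kg or 20 score points matter.* They are trivial.

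**Conclusion.** The concern holds in three places. The escalation conflict carries the most weight and should be fixed. It applies to infants with exactly one of the two findings who have not met the Section 3.5 stop criteria, and it changes their exposure by at most about 1.9-fold. That bound assumes a full 72 h course and a held infant who never escalates. How many infants this covers cannot be derived from the documents.

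The two gaps in Section 5.5.3 are real on a literal reading and worth correcting, but their effect on monitoring is limited by the other reporting routes. The Manual of Procedures (MOP), to which Section 3.5 refers for its definitions, was not available and may already settle some of this.

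**What to change.** 1. Change the synopsis and the Figure 6 legend to the Section 4.2.5 Dose rule, stating that either finding blocks escalation.
2. Add to Section 5.5.3(b) the mean BP fall of more than 30 mmHg from Section 3.5.
3. Add severe and life-threatening extracranial hemorrhage, as defined in Section 3.5, to the Section 5.5.3 list.

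Check the MOP for the same wording. Two further edits are optional tidying: align the synopsis hypotension stop with Sections 3.5 and 4.2.5, and correct item (iv) of the Section 4.2.5 discontinuation list, which repeats intracranial bleed from item (i). The trigger threshold and the ultrasound window need no change.

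The cost is wording, with no added scans or patients. Compared with the synopsis rule, some infants will stay at the lower dose. A few more events may count towards the DSMC discussion.

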5.5.3.1 Monitoring Enrollment

Because the focus of the study is to evaluate changes in oxygenation and determine the feasibility of conducting a larger randomized trial, the DSMC will routinely review enrollment rates on this study to assess whether the enrollment rates are likely to be insufficient to support a full randomized trial to determine the impact of milrinone on survival without ECMO. For the current pilot trial, we anticipate 3 patients to be enrolled per month. Given this accrual target, it is anticipated that at least 12 patients will be enrolled in the 6-month period after at least 75% of sites have begun randomization *and enrollment*.

This study will provide valuable data about CDH patients, response to various pulmonary vasodilators and pulmonary / nutritional outcomes at 12 months of age. Since this is a pilot trial to determine feasibility of a larger trial examining survival without ECMO as the primary

outcome, the interim efficacy of the Milrinone with respect to oxygenation will not be used as a criterion for stopping the study.

5.5.3.2 Future Plans:

Information obtained from this trial will be used for designing a definitive trial with a primary outcome of survival to discharge (or day 120, whichever is earlier) without ECMO. Preliminary sample size for the definitive trial is 752 (376 patients in each arm) and will require international collaboration (16 patients enrolled per month to complete the trial in 4 years).

SECTION 6. REFERENCES

(1997). "Inhaled nitric oxide and hypoxic respiratory failure in infants with congenital diaphragmatic hernia. The Neonatal Inhaled Nitric Oxide Study Group (NINOS)." *Pediatrics* **99**(6): 838-845.

Abman, S. H., J. P. Kinsella, E. B. Rosenzweig, U. Krishnan, T. Kulik, M. Mullen, D. L. Wessel, R. Steinhorn, I. Adatia, B. Hanna, J. Feinstein, J. Fineman, U. Raj and T. Humpl (2012). "Implications of the FDA Warning Against the Use of Sildenafil for the Treatment of Pediatric Pulmonary Hypertension." *Am J Respir Crit Care Med*.

Aggarwal, S., P. T. Stockman, M. D. Klein and G. Natarajan (2011). "The right ventricular systolic to diastolic duration ratio: a simple prognostic marker in congenital diaphragmatic hernia?" *Acta Paediatr* **100**(10): 1315-1318.

